# 7.0 International Research (where data collection will occur outside the United States and U.S. territories, including online activities)

International participants, excluding those from the European Economic Area, may be enrolled if they meet all eligibility criteria, including using English as their primary language. Similar to domestic participants, international participants will join all study visits using the iPad provided for them. All data collection will take place from Northwestern University and our approved collaborator at OHSU. An external IRB review will not be obtained since Northwestern will remain the primary study site. In accordance with Northwestern's policy, the Institution's human research activities, regardless of whether the research is subject to the U.S. Federal Policy for the Protection of Human Subjects, will be guided by an assurance of specific principles governing the institution in carrying out its responsibilities for protecting the rights and welfare of humans in research conducted at or sponsored by the institution.

### **8.0** Procedures Involved:

[figure not shown]
Eligible participants will be enrolled in this study for up to 18 months. Blocks 1 and 2 will last about 3 months each, with an approximately 4-month break between each block. After Block 2, there will be an approximately 4-month break. Block 3 will last about 1 month.

Participants will be mailed an Apple iPad, Apple Smart Keyboard, and Apple Pencil to keep for the duration of the study. The study team will use secure tablet shipping boxes through FedEx to deliver and track shipments. The Apple equipment will be used to

connect for study visits and to complete home exercises assigned during the study. When the participant has completed the study, they will be a sent a FedEx shipping label to return the Apple equipment in the box they were originally shipped in.

## **Orientation and Training**

Participants and communication partners will receive an orientation to the technological aspects of the study. During this session, both the participant and the communication partner will be consented to the study, provide updated demographic and health information, and learn the technological components of the iPad and study web application. This web-application is the main resource for the study and is where individuals access their therapy sessions, instructional videos and resources, and interactive web exercises.

After the orientation, participants and communication partners will go through a series of Blocks. In Blocks 1 and 2, there will be a pre- and post-evaluation, consisting of a series of neuropsychological measures and/or questionnaires. Blocks 1 and 2 will contain 5 therapy sessions and 2 social work sessions. Block 3 will consist of an evaluation with neuropsychological measures and questionnaires followed by three discharge sessions. The battery may be reduced at any timepoint based on the study team judgment of participant burden and ability. Neuropsychological measures will require at least a 6-month gap between administration.

- 1) Neuropsychological Testing. Participants with PPA will complete neuropsychological tests relevant for assessing cognition with a particular focus on language abilities for individuals with primary progressive aphasia. Administered by a research coordinator. See appendix.
- 2) Questionnaires. A research coordinator will administer the questionnaires to the participant at the neuropsychological testing session. The communication partner may assist the participant with PPA in completing the questionnaires if needed. The communication partner will also fill out self-report questionnaires including measures of communication/behavioral/cognitive abilities of the individual with a diagnosis and estimates of caregiver burden. Assistance will be provided from the study team as requested. See appendix.

- 3) Speech-Language Pathology (SLP) Evaluation. At this evaluation, the SLP will complete several assessments for assessing language abilities for individuals with primary progressive aphasia. They will also discuss personal goals (participant and communication partner), current challenges related to their diagnosis, and therapy expectations. See appendix.
- 4) Speech-Language Pathology (SLP) Therapy Sessions. Sessions are approximately 1 hour long. The sessions will be composed of impairment-based strategies (e.g., script training and training of target-words), compensatory-based strategies, and other related strategies and tasks as deemed appropriate by the SLP. The SLP, the participant with PPA, and the communication partner will collaboratively identify the most appropriate strategies to focus on based on other evidence-based therapy approaches (conversation strategies, impairment-based strategies, compensatory strategies). During therapy sessions, the communication partner is engaging as a co-participant in the intervention.
- 5) Social Work Sessions. Sessions are approximately 1 hour long. The first session will include an in-depth psychosocial assessment with the participant and their communication partner. Areas of discussion will include how the participant and family are coping with PPA symptoms and changing roles, their understanding of the diagnosis, the health of their family relationships along with emotional, social and financial resources, overall strengths and challenges and the need for community services. The participant, family and social worker will work collaboratively to identify needs and tailor plans for future sessions to address the most concerning identified needs.

## 9.0 Research with Vulnerable Populations

Vulnerable Populations: Individuals with Primary Progressive Aphasia are cognitively impaired. However, individuals in the mild stages of Primary Progressive Aphasia have deficits primarily in the use of language. Memory, attention, and other cognitive abilities are preserved. When the individuals enrolled or were screened in the related study, they were verified as being in the mild stages of the disease through medical records and a brief evaluation by our team. Although some disease progression is expected, we anticipate (based on more than 15 years of working with this population) participants will be able to understand and complete the consent process. We will gather medical records and conduct a screening for the individuals placed on the waitlist and new persons who contacted the study team after enrollment closed for the related study to determine eligibility. To aid with comprehension, participants with PPA will be consented with their communication partner. Their communication partner will also be consented into the study. This study provides an intervention for a population that has no pharmacological treatment for their disease, and thus a benefit for them to more effectively cope with their symptoms.

Individuals will be provided with the opportunity to speak with members of the study team, including speech-language pathologists, prior to consent and enrollment to ask any

questions they have. The study team members, including SLPs and social workers, are trained in communicating with individuals of this population.

To confirm that participants have the ability to provide their own consent, individuals with PPA will complete a consent assessment task with the research coordinator after reviewing the consent from. The task will prompt the participant to respond, either verbally or by pointing, to yes or no questions regarding information discussed in the consent form. If nonverbal answers are provided, the communication partner will aid in relaying the participant's gestural answers. During this task, the research coordinator may need to provide clarification on any areas of confusion. This assessment task will provide documentation of the participant's understanding and consent (see supporting documents). The assessment task template is based on a task used in the ACT NOW international clinical trial (NCT00831740).

During the first visit of Block 2 and Block 3, the research coordinator will confirm participants; understanding of their involvement in a research study. The research coordinator will complete the consent confirmation task (see supporting document) and document PT's decision. If the participant expresses confusion, the research coordinator will re-administer the consent assessment task and provide any clarification needed. The consent confirmation task and updated consent assessment task, if needed, will be stored in the participant's study file on FSMresfiles.

## **10.0** Incomplete Disclosure or Deception:

N/A

#### 11.0 Consent Process:

Both participants (individuals with PPA and their communication partners) will be consented verbally over video-chat with a research coordinator. The consent forms will be housed within REDCap. There will be two separate consent forms for individuals with a PPA diagnosis. Participants who were seen at NMH's Neurobehavior and Memory Clinic will have a HIPAA authorization in their consent form to grant approved study team members access to their medical records through an Enterprise Data Warehouse (EDW) exception. Participants who were not seen at NMH will be asked to send in their own medical records and will not require a HIPAA authorization. Participant consent forms that contain HIPAA authorizations must be retained for at least 6 years after completion of the study.

During this video-chat consent, participants will have the study explained to them in detail and they will have ample time to ask for questions or clarifications. A research coordinator will go through the REDCap consent (sent via link to the participant) with the participants. After reviewing the forms, the research coordinator will administer the consent assessment task to ensure the person with PPA's understanding and consent to participate. The participants will electronically sign the consent forms. Participants will be emailed their signed informed consent from REDCap after completion of the form.

Participants (individuals with PPA and their communication partners) will be asked to consent to an optional element on the consent form that asks if they would be willing to allow their audio and/or video recordings from sessions to be used in scholarly presentations or publications. These recordings could potentially be shown at disease-related conferences and speech-language pathology professional conferences in order to help professionals in the field understand the research and/or aid in training purposes. Because of the unique and rare presentation of PPA, speech samples and/or video recordings that display the effortful motor movements in producing words are often the best way to convey how the disease presents itself. In order to thoroughly explain our research methods and describe the speech therapy strategies used, it will be most beneficial to provide audio and/or video recordings during presentations to explain what written or verbal text cannot accomplish. If the participant answers "I agree," he or she is indicating they understand the risks associated with identification.

Participants (individuals with PPA and their communication partners) will complete an optional section on the consent forms that asks if they will allow their identifiable data to be shared with Mesulam Center faculty, staff, students, or approved collaborators for use in future studies. Participants will initial whether they agree or disagree on the REDCap form via the electronic signature function in REDCap.

Participants (individuals with PPA and their communication partners) will complete an optional section on the consent forms that asks if the PI can contact them in the future to see if they are interested in participating in other research studies by the PI. Participants will initial whether they agree or disagree on the REDCap form via the electronic signature function in REDCap.

# 12.0 Waiver of Participant Signature on Consent Form:

N/A

## 13.0 Waivers and Alterations of Consent Information:

N/A

# 14.0 Financial Compensation:

N/A

## 15.0 Audio/Video Recording/Photography

All study visits will take place online through a HIPAA-compliant Zoom license, provided by Northwestern for the Communication Bridge email account. All visits will be audio and video recorded for internal data collection purposes. The recordings are essential for data collection and analysis. Due to the language impairments present in PPA, participants and SLPs often communicate through nonverbal language (i.e., gestures, typed visual aids) during study visits. The therapy tasks being completed require us to watch visual indicators during data analysis. The data are used for intervention fidelity assessments that are conducted over the duration of the protocol. The

audio and video recordings are used to verify responses to uphold data rigor and integrity. Additionally, the recordings are used for continuous trainings of study personnel.

Participants and communication partners must consent to have their audio and video recorded for data collection purposes to participate in this study. There is an optional element in the consent form asking participants for permission to use audio and/or video recordings for use in scholarly presentations or publications.

All video files will be stored on FSMresfiles on locked computers and will be coded by study identity. Video recordings will not be saved to the Zoom cloud. The recordings themselves will not be deidentified. Portions of the recordings will be transcribed in order to complete therapy tasks and fulfill data collection (i.e., speech therapy strategies that incorporate script training and scoring). These transcriptions will be coded by study identity and stored on FSMresfiles. Only the PI and approved study personnel will be able to access these files. Recordings will be saved for as long as may be necessary to protect any intellectual property resulting from the work.

### **16.0** Potential Benefits of this Research:

By participating in this study, participants will learn new strategies for coping with their communication difficulties caused by the disease. These strategies may allow the individuals to engage more actively in their lives by facilitating communication. Due to the progressive nature of the disease, individual's communication will get worse over time and is known to impact psychosocial wellbeing of families. This current study is important in determining the duration of potential benefits of a multi-component intervention beyond the speech language therapy intervention studied in the related protocol.

Information learned in this research will provide valuable knowledge for the speech therapy community regarding treatment for moderate to late stages of PPA.

## 17.0 Potential Risks to Participants:

The risks for participation in the proposed research are minimal. Potential adverse events associated with this research include:

- 1. Loss of confidentiality
- 2. Fatigue and/or frustration in performing the online intervention
- 3. Depression and Anxiety: Caregivers of individuals with PPA and living with PPA can both be psychologically taxing experiences. It is not abnormal for individuals in these circumstances to express negative emotions, including hopelessness, sadness, anger, or frustration. It is important to recognize when these symptoms go beyond what is normally expected.

These risks will be minimized in the following ways:

1. Data will be stored securely, and any data sharing agreements will adhere to NU's strict policies on privacy protection.

- 2. This risk of fatigue is considered to be minimal and is addressed in the consent form. Fatigue will be minimized by advising the participant and caregiver that they should rest if they feel fatigued, before continuing with any component of the intervention. Participants will be working with licensed speech-language pathologists who are trained to identify fatigue and frustration and they will modify the plan accordingly. Participants will be informed of this risk when consenting to join the study.
- 3. The risk of depression and anxiety is considered to be minimal. Depression and Anxiety measures are completed with both the participant and communication partner at every evaluation. Specifically, the CAT-version of the PROMIS Depression and Anxiety Sub-tests are given to participants and communication partners (Cella et al., 2010). If the measures reveal aclinically relevant level of anxiety or depression (based on normative values), the research team will follow a risk-specific protocol outlined in the Risk Identification and Response Plan. The Risk Identification and Response Plan identifies unanticipated risks that go beyond what is expected in this study. However, if any verbal/behavioral indication of suicidal/homicidal thoughts are observed by the speech-language pathologists in the study, measures will be taken to alert the appropriate people. A licensed clinical social worker, [name]., is a Co-Investigator on this study. She will be consulted according to the plan and will meet with our participants for a session. Since [name] is a member of the study team, this information will be kept with the participant records.

# 18.0 Provisions to Protect Participant Privacy and Data Confidentiality:

All of the data and materials collected are for research purposes only, and data will be kept in strict confidence. No information will be given to anyone without permission from the participants. The consent form includes the informed consent statement required by the IRB of NU for clinical studies of cognition. The consent form will explain that only the PI and approved study personnel will have access to medical records and personal identifiable information. Participants will be given the opportunity to ask questions and will be provided with a signed copy of their consent form. All data collection will occur over a HIPAA-compliant Zoom software. Participants will be given a unique meeting ID for each study visit that only study personnel will have access to.

Medical records will be sent to the study team by the participants, if they are not seen by a doctor affiliated with Northwestern Memorial Hospital. Participants who were seen at NMH will consent to have their medical records shared with the study team for review by completing the HIPAA Authorization on the consent form. No one outside the PI or study team will have access to the medical records.

Data will be collected, entered, and stored securely in REDCap (Research Electronic Data Capture) database using the subject ID number. REDCap is a secure, web-based application for building and managing online data capture for research studies. Data will be de-identified through the use of the assigned study ID number and entered into the

password protected REDCap database within 48 hours of collection. All participant data are checked for accuracy. Data are maintained in a format that is easily transferred to statistical software for analysis. The database will be password protected and accessible only to the principal investigator and study personnel. Paper copies of any measures will be kept in locked files in our research offices and will only be accessible to the PI and study personnel. Northwestern University is a member of the REDCap consortium and the services are made available for this project through our CTSA-funded NUCATS Institute.

Data from the web-application will be constructed using an industry-standard software platform (PostgresSQL, Ruby on Rails, Apache, Linux). Data obtained through the web-application infrastructure will be stored and managed by Table XI, a product development and software consultant firm, and will be protected via IP restriction and on a Virtual Private Network accessible only to study-authorized staff. Data from the web-application will be stored using the participant's study ID number. Performance data from the web-application (e.g., Picture Cards accuracy) can be downloaded according to the participant study ID by the PI or approved study personnel into files that are easily used for data analysis (e.g., .csv, .xls). All access to this application will be provided over encrypted-TLS communication and all servers are locked and managed in a physically secure facility with Marlok identity management.

## 19.0 Data Monitoring Plan to Ensure the Safety of Participants:

An adverse event (AE) is any untoward medical occurrence in a participant during participation in the clinical study that is attributed to the cognitive testing or the engagement in the online therapy intervention. An adverse finding can include a sign, symptom, abnormal assessment, or any combination of these. While all adverse events will be reported, some may be expected due to the participant's medical condition. Each adverse event will be classified as being attributable or not to participation in the study. A serious adverse event (SAE) is any AE that results in one or more of the following outcomes that are attributable to participation in the study:

- · Death
- · A life-threatening event
- · Inpatient hospitalization or prolongation of existing hospitalization
- An important medical event based upon appropriate medical judgment

Grading Scale: AEs will be labeled according to severity, which is based on their impact on the participant. An AE will be termed "mild" if it does not have a major impact on the participant, "moderate" if it causes the participant some minor inconvenience, and "severe" if it causes a substantial disruption to the participant's well-being.

Study Relatedness Criteria: AEs will be categorized according to the likelihood that they are related to the study intervention. Specifically, they will be labeled definitely unrelated, definitely related, possibly related, or probably related to the study intervention.

Reporting and Follow Up: AEs will be reported by severity, relatedness to the intervention, action taken and outcome. Each adverse event will be reported separately. All AE reports and annual summaries will be de-identified and will not include participant-identifiable material. The PI will engage in continuous close monitoring of research participants with reporting of AEs to the Northwestern University Institutional Review Board.

SAEs that are unanticipated, serious, and possibly related to the study intervention will be reported to Northwestern University's IRB within 24 hours of notification of its occurrence.

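### Section 19.0's adverse-event definition does not cover loss of confidentiality, which Section 17.0 lists as a potential adverse event, and does not say whether communication partners count as participants

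*Protocol*

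**What the plan says.** Section 17.0 of the protocol introduces its list with "Potential adverse events associated with this research include". The first item is "Loss of confidentiality", the second is fatigue or frustration, and the third is depression and anxiety. The third item covers both roles: "Caregivers of individuals with PPA and living with PPA can both be psychologically taxing experiences". The same section has the PROMIS depression and anxiety measures given to both roles at every evaluation. A clinically relevant score leads to the Risk Identification and Response Plan.

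Section 19.0 defines what is graded for severity, classified for relatedness and reported to the IRB. The definition reads "An adverse event (AE) is any untoward medical occurrence in a participant during participation in the clinical study" and continues "that is attributed to the cognitive testing or the engagement in the online therapy intervention". It adds: "An adverse finding can include a sign, symptom, abnormal assessment, or any combination of these".

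The protocol uses the word *participant* in two ways. Section 11.0 includes the partner: "Both participants (individuals with PPA and their communication partners) will be consented verbally over video-chat with a research coordinator". Sections 8.0 and 17.0 repeatedly name the participant and the communication partner side by side, as two different people. Section 19.0 does not say which usage it follows.

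**The concern.** The section that names the expected harms and the section that defines the harms to be recorded do not match, in the type of event and possibly in the person. A coordinator who applies Section 19.0 as written has no basis for recording a confidentiality breach as an AE. Two coordinators could also treat the same partner's raised PROMIS score differently and both be following the protocol.

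Confidentiality is a relevant exposure here. Section 15.0 has every visit recorded on audio and video, and says of the files: "The recordings themselves will not be deidentified". Web-application data are held by an outside firm (Section 18.0), and iPads are shipped to and from homes (Section 8.0). A statement that no AEs occurred could therefore be true under the definition even though a breach had taken place. Partner events could be in or out of the count depending on who completed the form.

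**Working it through.** No arithmetic decides this point, and the protocol gives no figure to reproduce. The check sets the sections side by side.

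1. **Type of event.** Take the three items in Section 17.0 and test each against Section 19.0.
   - Fatigue or frustration can be a symptom, so it fits.
   - Depression and anxiety can be a symptom or an abnormal assessment, so they fit.
   - Loss of confidentiality is not a medical occurrence, whoever suffers it. The sentence on adverse findings says what they *can include*, so that list is open. It does not remove the word *medical* from the definition above it. The serious outcomes listed in Section 19.0 are also all medical.

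   One of the three named events therefore does not meet the definition, on either reading of *participant*.

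2. **Another route for a breach.** Sections 15.0, 18.0 and 20.0 describe storage and access controls. None says how a breach is recorded or reported. Section 19.0 is the only event-reporting route that the protocol sets out.

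3. **Person covered.** Section 11.0 counts partners as participants, and does so again in its paragraphs on optional consent. Section 8.0 calls the partner a co-participant in therapy, but elsewhere sets the two roles apart, as does Section 17.0. Within Section 19.0 the only clue is a remark that some events may be expected from the participant's medical condition. This leans towards the person with PPA but does not settle the matter.

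4. **What happens to partner distress.** Partners complete the PROMIS measures at every evaluation. Section 8.0 gives a pre- and a post-evaluation in each of Blocks 1 and 2 and one evaluation in Block 3: 2 × 2 + 1 = 5, fewer if the battery is reduced. A clinically relevant score triggers the response plan. The protocol does not say whether that score is also entered as an AE.

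5. **Scale.** Section 3.0 allows up to 30 people with PPA and their partners. Assuming one partner each, AE recording covers up to 30 people on the narrow reading and up to 30 + 30 = 60 on the wide one. This shows how many people the undefined word affects. It does not measure any effect on a result.

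**The case against.** The strongest reply is that partners are not shown to be excluded. The protocol's only explicit explanations of the word, in Section 11.0, include them. Section 17.0 is about risks to participants and itself lists caregiver distress. Naming participants and partners side by side may be ordinary shorthand. A raised PROMIS score fits an abnormal assessment. This stands: a reader might infer that Section 19.0 leaves partners out, but the documents support only that it does not say.

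Second, partner distress is screened at every evaluation and acted on, with a social worker consulted. This also stands. The open question is recording and counting. The response plan is not among the documents, so whether it links to AE recording cannot be determined.

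Third, the clause that restricts AEs to those "that is attributed to the cognitive testing or the engagement in the online therapy intervention" may matter more for partners than the word *participant*. Distress caused by the disease would fall outside the definition even if partners were named. That is right for such cases, and the clause has a difficulty of its own: Section 19.0 later sorts AEs into attributable or not. It does not rescue the confidentiality item, since a server or courier breach is hard to attribute to testing or therapy.

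Fourth, safeguards are in place: video files are coded by study identity, kept off the Zoom cloud and restricted to approved staff, and shipping is tracked. These make a breach less likely but do not bring one within the definition.

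**Conclusion.** The point holds in two parts of different strength. For loss of confidentiality it is a plain inconsistency: Section 17.0 calls it a potential adverse event, the Section 19.0 definition does not cover it, and the protocol gives no other recording route. For communication partners it is an ambiguity: the word is used both ways and Section 19.0 does not choose.

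The consequence is that AE reports *could* omit a breach and *could* count partner events inconsistently. A reader might go further and say that the safety result understates harm by definition, or that incomplete counts would undermine the feasibility claim. The documents do not support either. Partners may well be covered, and the protocol ties no feasibility criterion to AE counts. Nor can the gap be expressed as a rate of missed events, because no event frequencies are given.

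The conclusion rests on reading *medical* in its ordinary sense and on the protocol alone. The response plan or institutional rules may supply a recording route that is not visible here. The change is worth making because it is cheap and the contradiction is in the protocol's own text.

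**What to change.** In Section 19.0, state two things. First, AEs include the non-medical events listed in Section 17.0, expressly loss of confidentiality. Second, *participant* in that section covers both the person with PPA and the communication partner. Add a role field to the AE form and tabulate AEs by role. The severity scale grades impact on the participant, so it can be used unchanged once the word is defined.

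Leave the attribution clause in place in this amendment and reconcile it separately with the later classification of AEs as attributable or not. That step should also settle how a breach in storage or shipping is treated, since it may not be attributable to testing or therapy.

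The cost is a short amendment and one form field. The downside is a possibly higher reported AE count, which tabulation by role makes interpretable.

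### Protocol section 19.0 builds attribution into the definition of an adverse event and then sorts adverse events by attribution, so one of its two classes is empty as written; the mild and moderate grades also overlap

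*Protocol*

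**What the plan says.** All the rules at issue stand in section 19.0 of the protocol (Data Monitoring Plan).

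- **AE definition.** The occurrence must be one "that is attributed to the cognitive testing or the engagement in the online therapy intervention".
- **Expected events.** "While all adverse events will be reported, some may be expected due to" the participant's medical condition.
- **Attribution step.** "Each adverse event will be classified as being attributable or not to participation in the study".
- **SAE definition.** An SAE is an AE that results in "one or more of the following outcomes that are attributable to participation in the study", followed by a list of outcomes that includes death and inpatient hospitalisation.
- **Relatedness scale.** For AEs, "they will be labeled definitely unrelated, definitely related, possibly related, or probably related to the study intervention".
- **24-hour rule.** "SAEs that are unanticipated, serious, and possibly related to the study intervention will be reported" to the IRB within 24 hours of notification.
- **Severity grades.** An AE is mild "if it does not have a major impact on the participant" and moderate "if it causes the participant some minor inconvenience". It is severe if it substantially disrupts well-being.

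No other section gives a different AE definition that would settle the matter.

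**The concern.** A causality judgement sits at the entrance to the definition and is then asked for again as a classification of what has already passed through. If the definition governs, an event judged unrelated at first sight never receives the AE label, so it is not graded, classed or reported as an AE. If the later sentences govern, it is an AE and is reported as not attributable.

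What reaches the IRB under the AE label therefore depends on which sentence staff follow and on the first assessor's view of cause. If similar events recurred, those set aside at first judgement would not be among the AEs whose attribution could be looked at again.

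The grade overlap is a separate and smaller matter. AEs are reported by severity, and two assessors could grade the same minor event differently while both follow the text.

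**Working it through.** No arithmetic applies, and the protocol gives no figure to reproduce. The check is to read the rules of section 19.0 against each other.

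**Step 1: the attribution classes.** The attribution step has two classes, attributable to participation or not. Every AE must, by definition, already be attributed to testing or online therapy. Both belong to participation, so every AE is attributable and 1 of the 2 classes is empty. If the second class is meant to hold events, the definition wrongly excludes them. The sentence expecting some AEs from the medical condition points the same way, since an event put down to the disease alone fails the definition.

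**Step 2: the referents.** Causality is judged against three differently worded things:

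| Rule | Referent |
|---|---|
| AE definition | testing or online therapy |
| Attribution step, SAE definition | participation in the study |
| Relatedness scale, 24-hour rule | the study intervention |

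Because the third referent is narrower than the second, the label for a definitely unrelated event is not strictly empty: an AE attributed to testing alone could carry it. Only the two-way attribution step has an empty class.

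**Step 3: example events traced through the rules.**

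| Event | Literal definition | Later sentences |
|---|---|---|
| Fatigue attributed to an online therapy session | AE, attributable | AE, attributable |
| Event attributed to cognitive testing alone | AE, attributable; possibly unrelated to the intervention | same |
| Hospitalisation put down to the disease | not an AE | AE, not attributable |

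Only the third row differs. On neither reading is that hospitalisation an SAE, because the SAE clause itself requires attribution, and on neither does it enter 24-hour reporting. The second row shows why the referent matters. If such an event were serious, it could be an SAE, being attributable to participation, yet fall outside the 24-hour rule, which asks about the intervention. It would still be an AE reported to the IRB.

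**Step 4: the SAE clause.** Attribution is required for an event to be an SAE, and the 24-hour rule then filters SAEs by relatedness again, against a different referent. These two filters need to be reconciled when the AE definition changes.

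**Step 5: the grades.** Mild is defined by the absence of a major impact, moderate by a minor inconvenience. A minor inconvenience is not a major impact, so it satisfies both.

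**The case against.** The strongest reply is that this is a drafting slip rather than two live rules. Three later statements (events expected from the condition, the two-way attribution step and the label for unrelated events) favour inclusive recording, and only one relative clause points the other way. The statement that all AEs are reported supports the same intent. That is fair as to intent, but a promise to report all AEs covers only what meets the definition, so it cannot widen it. The text still needs correcting.

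Several stronger readings may tempt a reader, and the documents do not support them:

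- **That unattributed events are never recorded.** Section 19.0 defines and reports AEs but contains no logging rule. Only the AE label and AE reporting are affected. Assessment data still go into REDCap (section 18.0), and clinically relevant depression or anxiety scores still trigger the Risk Identification and Response Plan (section 17.0).
- **That the SAE definition is a second contradiction.** Requiring attribution there is a stated choice in a study described as minimal risk. It calls for reconciliation with the 24-hour rule, nothing more.
- **That social work falls outside safety monitoring.** Section 1.0 and the Background place social work inside the intervention. Section 8.0 lists therapy and social work sessions separately, but that reads as shorthand for speech-language sessions.
- **That section 17.0 or the status of communication partners exposes further errors.** Section 17.0 lists risks and uses the term adverse events loosely when it includes loss of confidentiality. Section 11.0 counts partners as participants while other sections name them separately, which merits at most a clarifying word.

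**Conclusion.** The contradiction in the AE definition stands and should be fixed. It rests on one premise, that cognitive testing and online therapy are parts of participation, which the protocol's own procedures bear out. Its size can be stated only in terms of the wording: one of two attribution classes is empty as written, and three referents are used for causality. No event count follows from the documents, and under-ascertainment is possible but not shown.

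The grade overlap also stands. Both matters are confined to AE and SAE labelling and IRB reporting. No safety endpoint is stated, and the effectiveness and feasibility results do not turn on either. The protocol itself sets these definitions, so they are not something left to a statistical analysis plan.

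**What to change.** 1. Remove attribution from the AE definition, so that an AE is any untoward medical event during participation, whether or not it is thought to be related.
2. Assess relatedness afterwards against one stated referent, and use that referent in the attribution step, the relatedness scale, the SAE definition and the 24-hour rule.
3. In the same edit, reconcile the SAE clause with the 24-hour rule: state whether attribution belongs in the SAE definition, in the reporting filter, or in both on the same terms.
4. Reword the mild and moderate grades so that no event meets both. The current text places a minor inconvenience under moderate. Where it belongs is for the sponsor to decide, and any move should be stated openly.

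The cost is about one paragraph of protocol wording and slightly more events recorded as AEs, in at most 30 dyads.
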